10 DATA SHARING PLAN

This study will be conducted in accordance with the following publication and data sharing policies and regulations:

- Publications from this research will be made available to the public through the National Library of Medicine PubMed Central website within one year after the date of publication.
- This trial is registered at ClinicalTrials.gov and results from this trial will be submitted to ClinicalTrials.gov.
- Final datasets underlying all publications resulting from the proposed research will be shared outside of VA under the following conditions.
 - A de-identified, anonymized dataset will be created and shared. It will be made available upon written request to allow for re-analysis and validation of results. All identifiable information and identifiers (e.g., ID numbers) will be removed from the dataset prior to sharing. Any data involving identifiable information (e.g., appointment dates) will be included as summary data (e.g., appointment counts) only. Sharing will take place under a written agreement prohibiting the recipient from identifying or re-identifying (or taking steps to identify or re-identify) any individual whose data are included in the dataset.

11 DATA ANALYSIS PLAN

Qualitative feedback (e.g., interview responses and open-ended items) will be analyzed using a rapid qualitative analysis approach (Hamilton, 2013). Quantitative analyses for descriptive aims (e.g., fidelity, feasibility) will be analyzed using descriptive statistics (e.g., central tendency and spread statistics such as counts, means, ranges, and standard deviations). Quantitative analyses for patient outcomes will be analyzed using statistical modeling to establish effect size which will be evaluated in comparison with the a priori effect size of $d=.3$.

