1.2 SCHEMA

2 INTRODUCTION

2.1 STUDY RATIONALE

Functional impairment, limitation in social and occupational roles (Üstün & Kennedy, 2009), is a significant problem for Veterans. Across diagnostic categories, mental health symptoms are associated with functional impairment and difficulty with role-related task (Kazis et al., 1998; Löwe et al., 2008; Spitzer et al., 2006). Despite the availability of services, many Veterans with mental health symptoms do not engage in mental health treatment (Elbogen et al., 2013; Seal et al., 2010). ***Whole Health STEPS (Structured Tiered Engagement with Peer Support) is an innovative approach to engaging this population through combining two novel modalities to engage with Veterans, peer support and Whole Health, tailored for delivery in Primary Care Mental Health Integration (PCMHI) a platform designed to increase access to mental healthcare.***

This two phase pilot trial is designed to address two key objectives (1) evaluate the feasibility and acceptability of Whole Health STEPS and (2) evaluate the preliminary impact of Whole Health STEPS on patient outcomes.

- Phase 1 addresses objective 1 and will be an open trial (Eligible n=10) to test the feasibility of peer delivery in primary care and acceptability to Veterans to inform further manual adjustments. Feasibility of research procedures will also be evaluated to inform adjustments to the research protocol.
- Phase 2 addresses objective 2 and will be a pilot RCT with a waitlist control (Eligible n=44) to evaluate impact on functional impairment and feasibility for subsequent grant applications.

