3 STUDY DESIGN

3.1 OVERALL DESIGN

This study consists of a two phased clinical trial.

Phase 1 is an open trial establishing preliminary feasibility and acceptability of Whole Health STEPS and informing adjustments to the clinical manual. Participants will be followed for the duration of their participation in Whole Health STEPS, a period of approximately 2-3 months. Following phase 1 enrollment, the investigators will review the data, make adjustments to the Whole Health STEPS manual and research protocol as necessary, and proceed with enrollment in Phase 2.

Phase 2 is a 2-arm single-site pilot randomized clinical trial with a waitlist control evaluating Whole Health STEPS impact on patient outcomes and feasibility. Random assignment will be made by research staff following eligibility determination using a stratified permuted block design based on baseline functional impairment (mild-moderate functional impairment $IPF \leq 50$ vs. severe-extreme functional impairment $IPF \geq 51$). Participants will be followed for a period of approximately 4-5 months, 2-3 months will be participation in Whole Health STEPS and 2 months will be either be waitlist or follow-up depending on randomization outcome.

- Hypothesis 2a. Whole Health STEPS will demonstrate an effect size (d) > 0.3 on psychosocial functioning.
- Hypothesis 2b. Whole Health STEPS will demonstrate clinical feasibility including positive results on process outcomes, retention, fidelity, and appropriateness on stepped-care decision points.

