Construct/ Function	Assessment	Recruitment Admin Data	Baseline Part 1	Baseline Part 2	Each Session or Post-Session	Mid Assessment	Final Assessment	Post-Treatment*	Post-Study Admin Data
Sample Description, Recruitment, & Screening	EMR Patient Identifiers and Contact Information	X							
	Self-Report Contact Information		X						
	EMR Demographics	X							
	EMR Mental Health Screeners & Relevant Diagnoses	X							
	EMR Veteran Status	X							
	EMR Primary Care Team Information								
	EMR Medications	X							
	EMR Problem List	X							
	BOMC (for cognition/ orientation)		X						
	P4 Screener (for suicidality)		X						
	Preference for direct referral to behavioral health		X						
	Demographics Questionnaire			X					
Psychosocial Functioning (Primary Patient Outcome)	IPF (psychosocial functioning)		X			X	X		
Behavioral Health Symptoms	PHQ-9 (depression)		X			X	X		
	GAD-7 (anxiety)		X			X	X		
	LEC (PTSD)		X						
	Criterion A Assessment (PTSD)		X						
	PCL-5 (PTSD)		X			X	X		
	AUDIT (alcohol use)		X			X	X		
Other Peer Services Outcomes	EMR VA Healthcare and Social Services Appointments	X							X
	Self-Report non-VA Healthcare and Social Services Utilization		X			X	X		
	RAS-SF (recovery)			X		X	X		

	WAI (therapeutic relationship)							X	
Other Whole Health Outcomes	MILM (meaning in life)			X		X	X		
	QOLI (quality of life)			X		X	X		
	ACORN (resources)			X		X	X		
	WHGAT (Whole Health Goal Attainment)				X				
Whole Health STEPS Feasibility	Intervention retention								X
	Fidelity Checklist				X				X
	Peer Post-session feedback forms (also falls under acceptability)				X				
	Supervisor Post-session feedback forms (design/manual usability)				X				
	UE-ATR (safety)								
Whole Health STEPS Acceptability	Veteran post-session feedback forms				X				
	Veteran post-treatment feedback interview							X	
	CSQ (satisfaction)							X	
Research Feasibility	Recruitment and eligibility rates								
	Data Collection & Procedural Problems								
	Research retention								X

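### Hypothesis 2a promises to demonstrate d above 0.3, but the plan compares an estimated effect size with 0.3 and gives no interval; with 44 Veterans, crossing 0.3 cannot show that

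*Combined protocol and SAP*

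**What the plan says.** Section 3.1 sets out Hypothesis 2a: "Whole Health STEPS will demonstrate an effect size (d) > 0.3 on psychosocial functioning". The measure is the IPF, which the schedule in Section 6 lists under "Psychosocial Functioning (Primary Patient Outcome" and collects at baseline, mid and final assessments.

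Section 11 covers the analysis in one sentence. "Quantitative analyses for patient outcomes will be analyzed using statistical modeling to establish effect size", and the result is an "effect size which will be evaluated in comparison with the a priori effect size of" 0.3. The model, the contrast, the time point, the significance level and the interval are not given.

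On size and design, Section 2.1 says that Phase 2 "will be a pilot RCT with a waitlist control (Eligible n=44) to evaluate impact on functional impairment". Section 3.1 describes a "2-arm single-site pilot randomized clinical trial with a waitlist control", randomised by a "stratified permuted block design based on baseline functional impairment". The allocation ratio and any allowance for dropout are not stated. Under Section 3.3 the waitlist arm receives the intervention after a 2-month wait, so the randomised comparison with no intervention ends there.

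**The concern.** To demonstrate that an effect exceeds 0.3 is a claim about the true effect. The only comparison the plan offers is between an estimate and 0.3, with no statement of the estimate's precision. If the standard error is of the same order as 0.3, an estimate above that value is compatible with no effect, or even with harm.

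What is at stake is the conclusion on the main patient outcome. Followed as written, the plan would let the report say that Hypothesis 2a was borne out when the data could not bear that statement. Section 2.1 makes impact on functional impairment the purpose of Phase 2, alongside feasibility for later grant applications, so this sentence is likely to be read and relied on.

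**Working it through.** The plan states no power, standard error or error rate, so there is no figure of its own to reproduce.

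**Inputs from the documents.** 44 Veterans in the RCT (Section 2.1); two arms and the criterion d > 0.3 (Section 3.1); comparison of the effect size with 0.3 (Section 11).

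**Assumptions, none stated in the documents.** 1:1 allocation, so 22 per arm; full retention; d taken as the unadjusted between-arm difference divided by the SD. Dropout, unequal allocation and baseline adjustment are then varied.

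**1. Precision, 22 per arm.**
- Near d = 0: SE = sqrt(1/22 + 1/22) = 0.302; half-width 1.96 × 0.302 = 0.59.
- At an observed d: SE = sqrt(2/22 + d²/88). For d = 0.30 this is sqrt(0.0909 + 0.0010) = 0.303, so the 95% interval is 0.30 ± 0.594, or about -0.29 to 0.89.

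**2. Chance that the observed d exceeds 0.3.** The cut-off corresponds to t = 0.3/0.302 = 0.995 on 42 degrees of freedom.
- True d = 0: 16.3% (16.0% by the normal approximation, 15.8% with the Hedges correction).
- True d = 0.2, which also does not meet the hypothesis: 37.3%.
- True d = 0.5: 74.7%.

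**3. Sensitivity of the figure at true d = 0.**

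| Scenario | SE(d) | P(observed d > 0.3) |
|---|---|---|
| 22 per arm, unadjusted | 0.302 | 16.3% |
| 18 per arm, unadjusted | 0.333 | 18.7% |
| 15 per arm, unadjusted | 0.365 | 20.9% |
| 29:15 allocation, unadjusted | 0.318 | 17.6% |
| 22 per arm, adjusted, r = 0.5 | 0.261 | 12.5% |
| 22 per arm, adjusted, r = 0.7 | 0.215 | 8.2% |
| 22 per arm, adjusted, r = 0.8 | 0.181 | 4.9% |

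Unadjusted rows use the t distribution. Adjusted rows use the normal approximation, with SE = 0.302 × sqrt(1 - r²), where r is an assumed correlation between baseline and follow-up IPF. With 20% loss, the adjusted figures at r = 0.5 and 0.7 become 15.2% and 10.6%.

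**4. What would support a true d above 0.3.** Solve d - 1.96 × sqrt(2/22 + d²/88) = 0.3. At d = 0.92 the SE is 0.317 and the lower limit is 0.92 - 0.62 = 0.30. So the observed d must be about 0.92.

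**5. Does adjustment rescue the claim?** Take the most favourable row, r = 0.8. The half-width is 1.96 × 0.181 = 0.35, so an observed d of 0.30 has an interval of about -0.05 to 0.65. Ignoring the small d² term, an observed d of about 0.65 would still be needed for the lower limit to reach 0.3.

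**The case against.** The best defence is that this is a pilot. The synopsis puts feasibility and acceptability first, Section 2.1 calls the impact preliminary, and no go/no-go decision is tied to 0.3. Section 11 also does not say that the point estimate alone decides, and a model that uses baseline IPF is plausible because IPF is measured at baseline and randomisation is stratified on it.

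Much of this stands. A pilot need not be powered for efficacy. The 16% is one case in a range of about 5% to 21%. Comparing the estimate with 0.3 is the natural reading of Section 11, though not an explicit rule. What does not stand is that any of this supports the word demonstrate: no interval is planned, and step 5 shows that strong adjustment does not change the conclusion.

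A reader might infer more than the documents support:

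- **That a true d of 0.3 failing about half the time is a fault of the sample size.** An approximately unbiased estimate falls short of its own true value about half the time at any sample size. A true d of exactly 0.3 also does not satisfy a hypothesis of d > 0.3.
- **That an inflated d will be used to size the next trial.** Section 2.1 mentions subsequent grant applications but does not say that the observed d will set their sample size.
- **That a claim of benefit should require the interval to exclude 0.** That would put an efficacy test on a pilot with about 17% power at d = 0.3 (two-sided 5%, 22 per arm). Nothing in the plan calls for it.

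**Conclusion.** The concern holds as a mismatch between the claim and the evidence planned for it. With 44 Veterans, an observed d above 0.3 does not demonstrate a true d above 0.3. On the unadjusted figures, an observed 0.30 is compatible with anything from about -0.29 to 0.89, and a null intervention would pass about 16% of the time.

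The sizes rest on assumed 1:1 allocation, full retention and no adjustment. Dropout to 18 or 15 per arm raises the 16% to about 19% or 21%; adjustment at r = 0.5 to 0.8 lowers it to about 12.5% to 5%. The conclusion does not rest on them: whatever the standard error, an estimate only slightly above 0.3 has a lower confidence limit below 0.3.

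This should be fixed, because it is the only criterion for the main patient outcome and following it can give a wrong conclusion. It is not a fatal flaw: the trial is a pilot and no safety or stopping decision depends on the comparison.

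**What to change.** Reword Hypothesis 2a in Section 3.1 and the last sentence of Section 11 as estimation. Suggested text:

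> The randomised between-arm standardised difference in IPF, taken before the waitlist arm starts Whole Health STEPS, will be reported with its 95% confidence interval. The value 0.3 is a reference. An observed d above 0.3 will be described as compatible with a benefit worth testing, and not as evidence that the true d exceeds 0.3.

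The cost is a change of wording in two sections and a more modest claim. No extra patients, assessments or data are needed.
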